4.2 Exclusion Criteria

The subject will be excluded from the study if any of the following exclusion criteria are met:

1. Subject has an anatomically narrow angle, synechiae or evidence of prior inflammation, angle closure glaucoma, normal tension glaucoma, pseudoexfoliation syndrome or pigmentary dispersion syndrome with or without glaucoma, or secondary glaucoma.
2. Subject has corneal endothelial cell counts of less than 2000 cells/mm² (measured by noncontact specular microscopy) at the screening or baseline assessments.
3. Subject has central corneal thickness less than 500 µm or greater than 620 µm at the screening or baseline assessments.
4. Subject has IOP greater than 32 mmHg in either eye before randomization.
5. Subject has used topical ocular hypotensive medications as follows: prostaglandin analogs, β-adrenoceptor antagonists, α-adrenergic agonists, or epinephrine-related medications within 4 weeks before the first dose of investigational product; or pilocarpine or carbonic anhydrase inhibitors within 7 days before the first dose of investigational product.
6. Subject has a history of angle closure, ocular surgery, microinvasive glaucoma surgery device insertion, or laser surgery, except for the following procedures, which are allowed: uncomplicated cataract surgery, laser peripheral iridotomy with resultant angle of Shaffer grade 3 or 4, and postcataract neodymium-doped yttrium-aluminum-garnet (Nd:YAG) laser posterior capsulotomy. Cataract surgery and other procedures must have occurred a minimum of 3 months before randomization.
7. Subject has a history of significant ocular trauma or ocular disease including but not limited to moderate to severe dry eye disease that requires chronic treatment or punctal plugs.
8. Subject has evidence of ocular infection, inflammation, degeneration, or dystrophy at the screening or baseline assessments, including but not limited to moderate to severe blepharitis (mild blepharitis is allowed), conjunctivitis (allergic or infectious), corneal dystrophy (epithelial, stromal, or endothelial), corneal haze of grade 1 or greater based on the Hwang Grading Scale of Corneal Haze, corneal opacities, keratitis, uveitis, or vitritis.
9. Subject has retinal disease including but not limited to: moderate or severe nonproliferative diabetic retinopathy (NPDR) (early NPDR is allowed), proliferative diabetic retinopathy, intermediate or advanced dry age-related macular degeneration (AMD) (early dry AMD is allowed), all geographic atrophy, or all wet AMD.
10. Subject has any nonglaucomatous optic neuropathy or other significant nonglaucomatous ocular disease that is likely to affect visual function.

11. Subject has any corneal or ocular surface pathology in either eye that prevents proper IOP measurement, pachymetry, or other study data collection procedures.
12. Subject has had changes to their existing prescription medication regimen for chronic disease, including those medicines that affect IOP, within 14 days or 5 half-lives before screening, whichever is longer.
13. Subject has started any new prescription drug medication for chronic disease, including those medicines that affect IOP, within 14 days or 5 half-lives before screening, whichever is longer.
14. Subject has a history of corticosteroid use within 3 months before randomization, except for nonperiocular dermatologic use, which is allowed.
15. Subject has used belladonna alkaloids (scopolamine, hyoscyamine, atropine) within 7 days prior to randomization, cannabinoids or opioids within 28 days before randomization, or B-type natriuretic peptides within the past year before randomization; or a subject has an anticipated need for any of the aforementioned drugs/drug categories during the study.
16. Subject has used amantadine within 28 days before randomization.
17. Subject is unable to discontinue contact lens use during and for 60 minutes following instillation of study medication, during ophthalmologic examinations, and during study visits.
18. Subject has a current or relevant history of any physical, medical, mental, or psychiatric illness, disorder, or condition that may require treatment during the study and/or that may interfere with the subject complying with the study rules and procedures or completing the study.
19. Subject has any condition that presents undue risk from use of the investigational product, assessment tools, or procedures.
20. Subject is a woman who is pregnant (positive serum β -hCG pregnancy test at the time of screening), lactating, or less than 90 days post partum at randomization.
21. Subject has donated blood within 60 days before first dose of investigational product.
22. Subject has donated plasma within 28 days before first dose of investigational product.
23. Subject has used another investigational product within 30 days before the first dose of investigational product or is actively enrolled in a drug or vaccine clinical study.
24. Subject has a positive human immunodeficiency virus (HIV), hepatitis B surface antigen (HBsAg), or hepatitis C virus (HCV) antibodies screen.
25. Subject has a positive drugs of abuse screen or alcohol breathalyzer test.
26. Subject has been previously enrolled in this study.
27. Subject has known hypersensitivity or allergy to any of the ingredients of the investigational product.

28. Subject consumes more than 21 units of alcohol per week or is unable to refrain from alcohol consumption within 48 hours before a scheduled visit. (1 alcohol unit=1 beer or 1 wine [5 oz/150 mL] or 1 liquor [1.5 oz/40 mL] or 0.75 oz alcohol.)
29. Subject is unable to refrain from tobacco or any products containing nicotine within 8 hours before a scheduled visit.

4.3 Restrictions

1. Subjects should refrain from strenuous physical exercise from 48 hours before admission to the site and during the visit.
2. Subjects must refrain from alcohol from 48 hours before admission to the site and during the visit.
3. Subjects should refrain from foods or beverages containing caffeine/xanthine from 48 hours before admission to the site and during the visit.
4. During washout periods, subjects should attempt to limit the use of alcohol and tobacco or nicotine-containing products.
5. Subjects must avoid using tobacco and other nicotine-containing products (smoking, chewing, patch, etc.) from 8 hours before admission to the site and during the visit.
6. Subjects must adhere to the restrictions on use of artificial tears as detailed in Section 5.2.2.

4.4 Reproductive Potential

4.4.1 Female Contraception

Sexually active females of childbearing potential must use an acceptable form of contraception throughout the study period and for 60 days following the last dose of investigational product. If hormonal contraceptives are used, they should be administered according to the package insert. Females of childbearing potential who are not currently sexually active must agree to use acceptable contraception, as defined below, if they become sexually active during the period of the study and 60 days following the last dose of investigational product.

Female subjects should be one of the following:

- Postmenopausal (12 consecutive months of spontaneous amenorrhea and age ≥ 51 years)
- Surgically sterile (having undergone one of the following surgical acts: hysterectomy, bilateral tubal ligation, bilateral oophorectomy, or bilateral salpingectomy) and at least 6 weeks after sterilization, or
- A female of childbearing potential with a negative serum β -hCG pregnancy test at the screening visit and before randomization. Females of childbearing potential must agree to abstain from sexual activity that could result in pregnancy or agree to use acceptable methods of contraception.

Acceptable methods of contraception are:

- Intrauterine devices plus condoms
- Double-barrier methods (eg, condoms and diaphragms with spermicidal gel or foam)
- Hormonal contraceptives (oral, depot, patch, injectable, or vaginal ring), stabilized for at least 30 days before the first dose of investigational product, plus condoms. Note: If subject becomes sexually active during the study, they should use one of the other acceptable methods noted above in addition to the hormonal contraceptive until it has been stabilized for 30 days.

4.4.2 Male Contraception

Male subjects will be required to use a condom in conjunction with spermicidal gel, foam, cream, film, or suppository from the time of first dosing until 60 days after the last dose of investigational product.

Childbearing female partners of male study participants will be required to follow the acceptable methods of contraception for this study (described in Section 4.4.1) from the time of first dosing until 60 days after the last dose of investigational product.

Male subjects must not donate sperm for 3 months after the last dose of investigational product.

4.5 Discontinuation of Subjects

A subject may withdraw from the study at any time for any reason without prejudice to their future medical care by the physician or at the institution. The investigator or sponsor may withdraw the subject at any time (eg, in the interest of subject safety). The investigator is encouraged to discuss withdrawal of a subject from investigational product with the medical monitor when possible.

If investigational product is discontinued, regardless of the reason, the early withdrawal evaluations listed in Table 1 are to be performed as completely as possible. Whenever possible, all discontinued subjects should also undergo the protocol-specified follow-up. Comments (spontaneous or elicited) or complaints made by the subject must be recorded in the source documents. The reason for termination and date of stopping investigational product must be recorded in the electronic case report form (eCRF) and source documents.

Randomized subjects who discontinue from the study may be replaced at the sponsor's discretion to ensure that at least 6 out of 7 subjects complete a dosing regimen cohort. Replacement subjects will be assigned to the same treatment group as the subject they are replacing.

4.5.1 Subject Withdrawal Criteria

At any time in the study, subjects will be discontinued from the study if the IOP measurement in either eye reaches a reading greater than 36 mmHg or a reading less than 8 mmHg. If the subject falls outside the above measurements, rescue treatment will be started by the investigator as per the current standard of care.

If subjects experience corneal hazing of grade 3 or greater on the Hwang Grading Scale of Corneal Haze, they will be discontinued from the study and standard of care will be initiated.

The early termination evaluations listed in [Table 1](#) are to be performed as completely as possible. Whenever possible, all discontinued subjects should also undergo the protocol-specified follow-up.

4.5.2 Reasons for Discontinuation

The reason for withdrawal must be determined by the investigator and recorded in the subject's medical record and on the eCRF. If a subject is withdrawn for more than 1 reason, each reason should be documented in the source document and the most clinically relevant reason should be entered on the eCRF.

Reasons for discontinuation include but are not limited to:

- Completed
- Adverse event
- Withdrawal by subject
- Noncompliance with investigational product
- Physician decision
- Study terminated by sponsor
- Lost to follow-up
- Pregnancy
- Protocol deviation
- Screen failure
- Other

4.5.3 Subjects “Lost to Follow-up” Prior to Last Scheduled Visit

A minimum of 3 documented attempts must be made to contact any subject lost to follow-up at any time point before the last scheduled contact (office visit or telephone contact). At least one of these documented attempts must include a written communication sent to the subject's last known address via courier or mail (with an acknowledgement of receipt request) asking that they return to the site for final safety evaluations and return any unused investigational product.

4.5.4 Stopping Criteria for Dose Escalation

1. Progressing from a dosing regimen cohort to the next or from a study part to the next will not occur in the presence of moderate or severe drug-related ocular AEs in 2 or more SHP639-treated subjects in a given cohort.
2. If 1 or more subjects experience corneal hazing of grade 3 or greater on the Hwang Grading Scale of Corneal Haze, they will be discontinued from the study. At that time, the study will stop for further evaluation by the Shire's Dose Escalation Committee.

3. If 2 or more subjects in a given cohort receiving active drug have a severe AE in the same organ or body system, no further subjects will be enrolled or dosed until further evaluation of the available data is made by the medical monitor and investigator to determine whether to stop or proceed with the study. Following a safety review of the event, study enrollment or dosing of currently enrolled subjects may be restarted if the medical monitor and the investigator determine that it is safe to proceed with the study.
4. If any other drug-related event occurs in subjects receiving active drug and is deemed to pose an unacceptable risk to subjects by the investigator or medical monitor after further evaluation, no further subjects will be enrolled or dosed until further evaluation of the available data is made by the medical monitor and investigator to determine whether to stop or proceed with the study. Following a safety review of the event, study enrollment or dosing of currently enrolled subjects may be restarted if the medical monitor and the investigator determine that it is safe to proceed with the study.

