6.2.3 Dosing

6.2.3.1 Dosing Procedures

After satisfying all screening and entry criteria for the study before dosing on Day 1 of each cohort, subjects will be randomized to receive either SHP639 ophthalmic solution or placebo, respectively. Investigational product (SHP639 ophthalmic solution or placebo) will be administered topically in 1 designated eye (Cohort A, SDTP only) or in both eyes (Cohort A, MDTP only, and Cohorts B, C, and D) at the time points specified in [Table 1](#).

Subjects will receive their assigned dose as dispensed by the pharmacist or designee at each site. Investigational product will be administered by the principal ophthalmologist or trained designee at each site while subjects are on site, and will then be self-administered by each subject for the remainder of the treatment period.

Subjects should receive the single dose or first dose if multiple daily dosing (depending on cohort assignment) each day between 7:00am and 9:00am. This is particularly important for cohorts C and D as these subjects will receive 3 and 4 doses daily.

In Cohort A only, there will be a SDTP and an MDTP. The 2 treatment periods will be separated by a washout period of 3-14 days. In Cohort A, single-dose administration of the corresponding dose level (concentration) will occur first, followed by the multiple-dose administration of the same dose level (concentration) QD. The dosing regimens for Cohorts B, C, and D will consist of multiple-dose administration of the appropriate dose level concentration BID, TID, or QID, respectively. For all cohorts, the final dose during the MDTP will be administered on the morning of Day 28.

In Cohort A only, as a safety measure, the first 3 subjects in the SDTP will be dosed with a minimum of 1-hour intervals between subjects. Subjects will then be observed overnight and until the next day (24 hours after dosing) with an ophthalmologist on call. If no AEs occur that are consistent with the predefined stopping criteria, dosing the rest of the cohort (Cohort A, single dose) will proceed as previously outlined. Designated study eye criteria are detailed in Section 3.1.1.

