Shire's Dose Escalation Committee will consist of, at a minimum, the coordinating principal ophthalmologist, the Shire medical monitor, and the Shire ophthalmic study physician. Additional team members may be included as needed.

At any time during the course of the study, subjects will be discontinued from the study if their IOP measurement reaches a reading of greater than 36 mmHg or a reading of less than 8 mmHg. Additionally, if subjects experience corneal hazing of grade 3 or greater on the Hwang Grading Scale of Corneal Haze, then they will be discontinued from the study. Should an event occur that requires a subject's discontinuation from the study, the study will be halted for further evaluation by Shire's Dose Escalation Committee.

The Dose Escalation Committee may authorize progression from 1 cohort to the next after the completion of the previous treatment regimen cohort and completion of the previous dose level cohort, as appropriate. Additionally, more than 1 cohort of safety data may be reviewed at a dose escalation meeting depending on scheduling and study progress. A minimum of 6 subjects should have completed the previous cohort(s) without clinically significant adverse changes; this includes findings on the ophthalmologic examination. Additionally, progression will not occur in the presence of moderate or severe drug-related ocular AEs in 2 or more subjects.

If, in the judgment of the coordinating principal ophthalmologist, the Shire medical monitor, and the Shire ophthalmic study physician, it is unclear whether there is a potential safety concern or whether dose escalation should occur, a dose level may be reduced, modified, or repeated depending on the outcome of the safety data review between doses or treatments. Further, based on the findings from the dose escalation review meetings, a cohort (or cohorts) may be determined to not be necessary to determine the safety of SHP639. Finally, upon completion of all dose cohorts, additional doses may be studied based on emergent safety, PD, and PK data following the necessary protocol amendment and Institutional Review Board (IRB) reviews.

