6.2.4 Unmasking the Treatment Assignment

The treatment assignment code must not be broken during the study except in emergency situations where the identification of the investigational product is required for further treatment of the subject. The investigator should contact the medical monitor as soon as possible after the investigator has been unmasked.

In the event that the treatment assignment code is broken and the date and signature of the person who broke the code are recorded in the IRT and the source documents. The reason for breaking the code will be captured in the clinical database. Upon breaking the code, the subject is withdrawn from the study but should be followed up for safety purposes. Any code breaks that occur must be reported to the contract research organization (CRO) and sponsor. Code-break information is held by the pharmacist/designated person at the site.

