8.1.2 Relationship Categorization

A physician/investigator must make the assessment of relationship to investigational product for each AE. The investigator should decide whether, in his/her medical judgment, there is a reasonable possibility that the event may have been caused by the investigational product. If there is no valid reason for suggesting a relationship, then the AE should be classified as “not related.” Otherwise, if there is any valid reason, even if undetermined or untested, for suspecting a possible cause-and-effect relationship between the investigational product and the occurrence of the AE, then the AE should be considered “related.” The causality assessment must be documented in the source document and the eCRF.

The following additional guidance may be helpful:

Term	Relationship Definition
Related	The temporal relationship between the event and the administration of the investigational product is compelling and/or follows a known or suspected response pattern to that product, and the event cannot be explained by the subject’s medical condition, other therapies, or accident.
Not Related	The event can be readily explained by other factors such as the subject’s underlying medical condition, concomitant therapy, or accident and no plausible temporal or biologic relationship exists between the investigational product and the event.

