9.3 Data Handling Considerations

Data that may potentially unmask the treatment assignment (ie, investigational product blood concentrations, antidrug antibody, treatment allocation, and investigational product preparation/accountability data) will be handled with special care during the data cleaning and review process. These data will be handled in such a way that, before unmasking, any data that may unmask study team personnel will be presented as masked information or otherwise will not be made available. If applicable, unmasked data may be made available to quality assurance representatives for the purposes of conducting independent drug audits.

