9.6 Sample Size Calculation and Power Considerations

A sufficient number of subjects will be screened to ensure the enrollment and completion of 84 subjects.

The number of subjects in this study is not based on statistical power considerations because the statistical analyses are primarily descriptive in nature. However, if at least 7 subjects complete each cohort, then there will be at least 65% to 85% probability of observing at least 1 occurrence of any AE with a true incidence rate for a given dose group of at least 15-25%, respectively.

It is estimated that dose escalation will occur for up to 3 dose levels (4 cohorts within each dose level). Each cohort will include 5 subjects randomized to active drug and 2 subjects randomized to placebo for an estimated total of at least 84 subjects.

For each cohort, the number of subjects will be increased as needed based on safety and IOP response. Any cohort can be repeated to confirm findings with regard to safety or IOP response.

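### Protocol 4.5.4 and 6.2.3.2 count different subjects for the same escalation stop, and the protocol does not say which count governs or whether the committee has treatment codes

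*Protocol*

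**What the plan says.** Protocol Section 4.5.4, item 1, rules out progression to the next dosing-regimen cohort or study part "in the presence of moderate or severe drug-related ocular AEs in 2 or more SHP639-treated subjects in a given cohort". Section 6.2.3.2, which describes the escalation meetings, says: "progression will not occur in the presence of moderate or severe drug-related ocular AEs in 2 or more subjects". It has no treatment qualifier and no cohort limit, and the same section allows one meeting to review more than one cohort.

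Section 9.6 fixes the numbers: "Each cohort will include 5 subjects randomized to active drug and 2 subjects randomized to placebo". A full cohort therefore has 5 countable subjects under 4.5.4 and 7 under 6.2.3.2.

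Three sets of provisions bear on how the counts can be applied:

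- **Relatedness.** Section 8.1.2: "A physician/investigator must make the assessment of relationship to investigational product for each AE". Section 6.2.3.1 shows that this term covers both arms: "Investigational product (SHP639 ophthalmic solution or placebo) will be administered topically".
- **Treatment codes.** Section 6.2.4: "The treatment assignment code must not be broken during the study except in emergency situations". A subject whose code is broken is withdrawn. Section 9.3 adds that, before unmasking, "any data that may unmask study team personnel will be presented as masked information or otherwise will not be made available".
- **Timing.** Under Section 6.2.3.2 a meeting may convene once at least 6 subjects have completed the 24-hour assessments (single dose) or the Day 14 assessments (multiple dose). Under Section 9.5 the first planned unmasking comes after Day 29 of Cohort B3, and later cohorts may be unmasked after their own Day 29.

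Item 3 of Section 4.5.4 is also tied to treatment received ("If 2 or more subjects in a given cohort receiving active drug have a severe AE in the same organ or body system"), and item 4 is similar.

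**The concern.** This stop helps decide whether a first-in-human study moves to a higher concentration or more frequent dosing. Two people applying two current sections of the protocol to the same cohort could reach different answers.

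The qualifier drug-related does not close the gap. An investigator rates relatedness to investigational product, so a placebo subject can have a related ocular event. Section 6.1 gives placebo the same excipients as the active solution, which is preserved with benzalkonium chloride.

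The 4.5.4 count also needs to know who received SHP639. The documents describe no route by which that information reaches the committee at a 24-hour or Day 14 meeting.

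**Working it through.** **1. The two counts side by side.** Let A be the number of affected SHP639 subjects (0 to 5) and P the number of affected placebo subjects (0 to 2) in one full cohort.

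- 4.5.4 is met when A ≥ 2.
- 6.2.3.2 is met when A + P ≥ 2.

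If A ≥ 2 then A + P ≥ 2, so the first implies the second. The counts disagree only for (A, P) = (1, 1), (1, 2) or (0, 2). In each of these 6.2.3.2 blocks progression and 4.5.4 item 1 does not.

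**2. How often they disagree.** The documents give no operating characteristic for this stop, so there is no figure to reproduce. I borrow the 15% and 25% adverse event rates from Section 9.6 as the active rate. They are general rates, not rates of moderate or severe related ocular events. No placebo rate is given, so I assume one between 0% and the active rate. Subjects are taken as independent, with A binomial on 5 and P binomial on 2.

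P(disagree) = P(A=1) × P(P≥1) + P(A=0) × P(P=2)

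Active 15%, placebo 15%:
- P(A=0) = 0.85^5 = 0.4437; P(A=1) = 5 × 0.15 × 0.85^4 = 0.3915
- P(P≥1) = 1 − 0.85² = 0.2775; P(P=2) = 0.15² = 0.0225
- 0.3915 × 0.2775 + 0.4437 × 0.0225 = 0.1086 + 0.0100 = 0.1186

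Active 25%, placebo 25%:
- P(A=0) = 0.75^5 = 0.2373; P(A=1) = 5 × 0.25 × 0.75^4 = 0.3955
- P(P≥1) = 1 − 0.75² = 0.4375; P(P=2) = 0.25² = 0.0625
- 0.3955 × 0.4375 + 0.2373 × 0.0625 = 0.1730 + 0.0148 = 0.188

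| Active rate | Placebo rate (assumed) | 4.5.4 met (≥2 of 5) | 6.2.3.2 met (≥2 of 7) | Disagree |
|---|---|---|---|---|
| 15% | 0% | 16.5% | 16.5% | 0% |
| 15% | 5% | 16.5% | 20.4% | 3.9% |
| 15% | 10% | 16.5% | 24.4% | 7.9% |
| 15% | 15% | 16.5% | 28.3% | 11.9% |
| 25% | 0% | 36.7% | 36.7% | 0% |
| 25% | 5% | 36.7% | 40.6% | 3.9% |
| 25% | 10% | 36.7% | 44.5% | 7.8% |
| 25% | 15% | 36.7% | 48.2% | 11.5% |
| 25% | 25% | 36.7% | 55.5% | 18.8% |

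A meeting may be held with 6 subjects. At equal rates of 15%, 6.2.3.2 is then met in 22.4% of cohorts, against 11.0% for 4.5.4 if 4 active and 2 placebo are present, or 16.5% if 5 and 1. At equal rates of 25% the figures are 46.6% against 26.2% or 36.7%.

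**3. What a masked total would show.** Suppose the committee sees only the total A + P among 7 subjects.

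- A total of 0 or 1: 4.5.4 cannot be met.
- A total of 4 or more: at most 2 are placebo, so 4.5.4 is met.
- A total of 2 or 3: undetermined without codes. If events are unrelated to treatment, the chance that at least 2 are active is C(5,2)/C(7,2) = 10/21 = 47.6% at a total of 2. At a total of 3 it is 1 − 5/35 = 30/35 = 85.7%.

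Over the same placebo range, a total of 2 or 3 arises in about 16% to 27% of cohorts at a 15% active rate and 35% to 48% at 25%.

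**The case against.** The best reply is that the sections do not conflict in operation. Both are prohibitions, and 4.5.4 item 1 never authorises progression when its own count is unmet. A committee that follows 6.2.3.2 never breaches 4.5.4. That stands. A reader might infer that the sections give opposite orders, or that following 6.2.3.2 could miss a stop that 4.5.4 requires; the text supports neither.

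Section 6.2.3.2 also asks that at least 6 subjects complete the previous cohort(s) without clinically significant adverse changes. Two affected subjects out of 7 leave at most 5, so the one-active, one-placebo case may fail there too. This stands as a possibility: the protocol does not say that every moderate or severe related ocular event is such a change.

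A reader might also infer that the Dose Escalation Committee is masked and so cannot apply the 4.5.4 count at all. The documents do not say so. Masking is an inference from the double-masked design, the emergency-only code-break rule, the data-handling rule and the absence of any named unmasked member. Even if it is right, only totals of 2 or 3 are unresolved.

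Nor is the count unavailable for every decision. SAP Section 13 unmasks the sponsor and CRO teams to Cohorts A and B at the interim analysis, and the footnote to SAP Figure 1 takes the B-to-C move out of the Day 14 meeting rule. Later cohorts could be decided with codes if the committee waited for the optional unmasking after Day 29.

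None of this tells the reader which count is the rule.

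**Conclusion.** The inconsistency is real and should be corrected. Two current sections state one escalation stop with different numerators and different cohort scope, and nothing says which governs. A case with one active and one placebo event separates them.

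In 7-subject cohorts the counts disagree in 0% to 11.9% at a 15% active rate and 0% to 18.8% at 25%. The upper ends require the placebo rate to equal the active rate. Quoting only those would overstate the point, since the disagreement vanishes when placebo subjects have no such events. The ranges rest on borrowed event rates, an assumed placebo rate and independence between subjects; the textual conflict rests on none of these.

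The second part is a gap: the documents give the committee no stated access to treatment codes at its 24-hour or Day 14 meetings. If it is masked, totals of 2 or 3 of 7 cannot be settled under 4.5.4, and items 3 and 4 of that section depend on treatment received in the same way.

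**What to change.** Reconcile Sections 4.5.4 and 6.2.3.2 so that both state the same numerator and the same cohort scope for this stop. State what access the Dose Escalation Committee has to treatment codes at each type of meeting. If the count is by treatment received, name who supplies it and how masking is kept for everyone else. Check items 3 and 4 of Section 4.5.4 against the same statement, since those are evaluated by the medical monitor and the investigator.

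The choice of rule is a clinical decision for the sponsor, and none is proposed here. The cost is protocol wording, plus a simple arrangement for supplying the count if it stays tied to treatment received. No extra subjects, visits or analyses are needed.
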